### 20. DMARDs:

- a. Cyclophosphamide ≤ 24 weeks from screening
- b.  $\leq$  weeks from screening.
- c. Antimalarials and conventional DMARDs:

  are allowed only if started > weeks before screening and at a stable dose ≥ weeks from screening. Combination therapies are not allowed.
- d. Biologic DMARDs: ≤ weeks from screening. Rituximab and other CD20 depleting monoclonal antibodies are not allowed ≤ weeks from screening.

## 21. IMP in another clinical study:

- a. Prohibited  $\leq 12$  weeks or 5 half-lives (whichever is longer), or for CD20 depleting monoclonal antibodies,  $\leq 24$  weeks or 5 half-lives (whichever is longer)
- b. Nonbiologic IMP: Prohibited  $\leq 12$  weeks or 5 half-lives (whichever is longer)
- c. Biologic IMP: Prohibited ≤ 24 weeks or 5 half-lives (whichever is longer) before screening
- 22. Chinese traditional medicine with known immunomodulatory action
- 23. Pharmacological topical ophthalmic agents (eg, non-steroidal anti-inflammatory drugs [NSAIDs], \_\_\_\_\_\_)

# **5.3.** Lifestyle Considerations

## **5.3.1.** Meals and Dietary Restrictions

No restrictions apply.

## 5.3.2. Caffeine, Alcohol, and Tobacco

No restrictions apply except for those described in the exclusion criteria (Section 5.2, exclusion criterion 8).

### 5.3.3. Activity

No restrictions apply.

### 5.4. Screen Failures

A screen failure occurs when a participant consenting to participate in the clinical study is not assigned to IMP. A minimal set of screen failure information (demography, screen failure details, eligibility criteria, SAE reports) is required to ensure transparent reporting of screen failure participants and respond to regulatory authority queries.

- Retesting: Participants with exclusionary clinical laboratory results, ECGs, vital sign measurements, etc that are inconsistent with their medical history or clinical evaluation can be retested within the remaining screening period to confirm the test value(s).
- Rescreening: Participants who do not initially meet this study's eligibility criteria may be rescreened once. For example, if the participant does not meet eligibility

criteria because of an acute illness ongoing during screening (considering the illness itself does not violate inclusion/exclusion criteria), they may be rescreened once the illness is resolved or the medical issue stabilized. Rescreened participants will be reconsented and assigned a new participant number for each rescreening event.

# 5.5. Criteria for Temporarily Delaying Enrollment

Not applicable.

# 6. STUDY INTERVENTION(S) AND CONCOMITANT THERAPY

All IMP is manufactured according to Good Manufacturing Practice regulations.

# 6.1. Study Intervention(s) Administered

**Table 2:** Study Intervention(s) Administered

Intervention label	Intervention label Efgartigimod IV		
Intervention name	Efgartigimod IV concentrate for solution	Placebo solution for IV infusion	
Intervention description	Sterile, colorless, clear concentrate solution for efgartigimod 20 mg/mL infusion	Sterile, colorless, clear concentrate solution for infusion, with the same excipients, but without the active ingredient (efgartigimod)	
Type	Biologic	Placebo	
Dose formulation	Infusion	Infusion	
Unit dose strength(s)	) 20 mg/mL Not applicable		
Dosage level(s)	10 mg/kg once weekly for 24 weeks	Placebo once weekly for 24 weeks	
Route of administration	IV infusion	IV infusion	
Use	Experimental	Placebo comparator	
IMP and NIMP/AxMP	IMP	IMP	
Sourcing	Centrally by the sponsor	Centrally by the sponsor	
Packaging and labeling	IMP will be provided in glass vials. Each vial will be labeled per country requirements.  IMP will be provided in Each vial will be labele country requirements.		
Former name	ARGX-113	Not applicable	

AxMP=auxiliary medicinal product; IMP=investigational medicinal product; IV=intravenous; NIMP=noninvestigational medicinal product

**Table 3:** Study Arm(s)

Arm title	IMP	Placebo
Arm type	Experimental	Placebo
Arm description	Efgartigimod IV 10 mg/kg once weekly for 24 weeks	Placebo IV once weekly for 24 weeks
Associated intervention labels	Efgartigimod IV	Placebo

IMP=investigational medicinal product; IV=intravenous

# 6.2. Preparation, Handling, Storage, and Accountability

The IMP will be supplied to the investigational site by the sponsor's designated IMP supply vendor.

The pharmacy manual provides detailed instructions on the preparation, handling, storage, accountability, and disposition of unused IMP.

The investigator or designee is responsible for the correct and safe storage of the IMP. All IMP must be stored in a secure, environmentally controlled, and monitored (manual or automated) area following the labeled storage conditions, with access limited to the investigator and authorized site staff.

The investigator or designee must confirm that appropriate temperature conditions have been maintained for all IMP received during transit. Any discrepancies are reported and resolved before using the IMP.

Only participants enrolled in the study may receive IMP, and only authorized site staff or designee may supply IMP.

Appropriate dilutions in a 0.9% saline solution in an infusion bag will be prepared before administration with an IV pump.

IMP must be stored refrigerated (2 °C to 8 °C) and protected from direct sunlight in secondary packaging. It should not be shaken or exposed to freezing temperatures.

Participants will be monitored for safety for  $\geq 30$  minutes after the end of IMP administration.

# 6.3. Assignment to Study Intervention

All participants will be randomized to IMP using IRT in a 2:1 ratio of efgartigimod or placebo, respectively.

Upon confirmation of eligibility at baseline, the participant will be randomized through IRT and stratified by IgG value at screening (> 16.0 g/L or  $\leq 16 \text{ g/L}$ ).

# 6.4. Blinding

This is a double-blinded study. The IRT will be programmed with blind-breaking instructions. In case of an emergency, the investigator is solely responsible for determining if unblinding of the IMP assignment is necessary. Participant safety must always be the first consideration in making such a determination. If the investigator decides that unblinding is warranted, the investigator may contact the sponsor to discuss the situation before unblinding a participant's IMP unless this could delay emergency treatment for the participant. If a participant's intervention assignment is unblinded, the sponsor must be notified within 24 hours of this occurrence. The date and reason for the unblinding must be recorded in the source documents.

# 6.5. Study Compliance

Participants will receive IMP under medical supervision at the site. The date and time of each dose administered will be recorded in the source documents. Documentation will include both start and end time of infusion.

At home visits (Section 1.3), IMP will be administered by a health care professional (nurse). The date and time of each dose administered will be recorded in the source documents.

Deviation(s) from the prescribed dosage regimen will be recorded.

Any participant who misses a scheduled dose ( $\pm 2$  days) will wait to receive the next scheduled dose (refer to Section 1.3).

### 6.6. Dose Modification

The maximum total efgartigimod dose per efgartigimod infusion is 1200 mg for participants weighing  $\geq$  120 kg. The IMP weight-based dose will be recalculated if a participant's weight has changed (increased or decreased) by more than 10% from baseline.

# 6.7. Continued Access to IMP After the End of the Study

At the end of the study, argenx will comply with all local laws and regulations to ensure participants have continued access to IMP considered medically essential.

At week 24 (visit 25) eligible participants will have the option to enroll in the OLE study, where all participants will be treated with efgartigimod IV.

Participants will be ineligible for OLE study enrollment if either of the following criteria apply:

- Permanently discontinued from IMP (regardless of whether the participant completed the study)
- Discontinued from the study

Participants who complete the week 24 (visit 25) visit while temporarily interrupted from IMP (refer to Section 7.1.1) may enroll in the OLE study at the discretion of the investigator. These participants will enter the OLE study but will not be dosed with efgartigimod IV until they meet the relevant conditions specified by the protocol for the OLE study.

## **6.8.** Treatment of Overdose

Any dose of efgartigimod > 10% of the intended weekly amount will be considered an overdose.

The sponsor does not recommend specific treatment for an overdose.

In the event of an overdose, the investigator or treating physician should:

- Evaluate the participant to determine, in consultation with the medical monitor, if possible, whether IMP should be interrupted.
- Closely monitor the participant for any AE/SAE and laboratory abnormalities (as medically appropriate and at least until the next scheduled follow-up).
- Record the overdose, the quantity of the excess dose, and the duration of the overdose in the eCRF.

# 6.9. Prior and Concomitant Therapy

Participants should stay on a stable regimen of medications throughout the study. Any medication or vaccine (including over-the-counter or prescription medicines, recreational drugs,

vitamins, and/or herbal supplements [including Chinese traditional medicine]) or other specific categories of interest that the participant is receiving at the time of screening, or receives during the study must be recorded. Any treatment used for pSS in the 6 months prior to screening should also be recorded.

Recording should include the following information:

- Reason for use
- Dates of administration, including start and end dates
- Dosage information (ie, dose and frequency)

The following medications or treatments are not permitted during the periods listed in Table 4.

**Table 4:** Prior and Concomitant Therapy

Medication Prior to study treatment period		Period participant is receiving IMP (Section 5.2)	Follow-up period	
Live or live-attenuated vaccines	Prohibited ≤ 4 weeks before screening	Prohibited	Permitted from 28 days after the last IMP dose	
SCIg	Prohibited ≤ 12 weeks before screening	Prohibited	Permitted	
IVIg	Prohibited ≤ 12 weeks before screening	Prohibited	Permitted	
Corticosteroid steroids:				
Intra-muscular or intravenous corticosteroids	Prohibited ≤ 4 weeks before screening	Prohibited	Permitted	
Oral corticosteroids	Permitted at stable dose up to 10 mg at least 4 weeks before screening	Dose up to 10 mg	Permitted	
Inhaled corticosteroids	Permitted	Permitted	Permitted	
Intra-articular steroids	Prohibited ≤ 4 weeks before screening	Prohibited	Permitted	
Topical steroids	Topical (non-ophthalmic) steroids are permitted  Topical ophthalmic steroids are prohibited.	Topical (non-ophthalmic) steroids are permitted  Topical ophthalmic steroids are prohibited.	Permitted	
DMARDs			·	
Conventional DMARDS / antimalarials			Permitted	

Medication	Prior to study treatment period	Period participant is receiving IMP (Section 5.2)	Follow-up period
Cyclophosphamide	Prohibited ≤ 24 weeks from screening	Prohibited	Permitted
Biologic DMARDS	Prohibited ≤ 12 weeks of screening Rituximab and other CD20 depleting mAbs: prohibited ≤ 24 weeks of screening	Prohibited	Permitted
Targeted synthetic DMARDs:			
	Prohibited ≤ weeks from screening	Prohibited	Permitted
IMPs:			
IMP in another clinical study	Prohibited ≤ 12 weeks or 5 half-lives (whichever is longer)  CD20 depleting mAbs: prohibited  ≤ 24 weeks or 5 half-lives (whichever is longer)	Prohibited	Permitted
Nonbiologic IMP in another clinical study	Prohibited ≤ 12 weeks or 5 half-lives (whichever is longer)	Prohibited	Permitted
Biologic IMP in another clinical study			Permitted
Other:			
Chinese traditional medicine with known immunomodulatory action	Prohibited	Prohibited	Permitted
Anticholinergic agents	Permitted at stable dose 4 weeks prior to screening or during screening	Permitted at stable dose	Permitted

Medication	Prior to study treatment period	Period participant is receiving IMP (Section 5.2)	Follow-up period
Topical symptomatic medications for pSS	Permitted	Baseline, week 16, week 24, and EDV/IMP discontinuation visits, participants will be required to withhold ophthalmic lubricants, ophthalmic lubricating ointments, hydroxyl cellulose ophthalmic inserts, and saliva substitutes before efficacy assessments are completed.	Permitted
Pharmacological topical ophthalmic agents (eg, NSAIDs, cyclosporine)	Prohibited	Prohibited	Permitted
Pilocarpine and/or any other pharmacological stimulant for salivary and lacrimal glands	Permitted at stable dose in the ■ weeks prior to screening	Permitted at stable dose	Permitted

; DMARD=disease-modifying antirheumatic drug; EDV= early discontinuation visit; IMP=investigational medicinal product; IVIg= intravenous immunoglobulin; NSAID=non-steroidal anti-inflammatory drug; pSS=primary Sjögren's syndrome; SCIg=subcutaneous immunoglobulin

# 7. DISCONTINUATION OF IMP AND PARTICIPANT DISCONTINUATION/WITHDRAWAL

Discontinuation of specific sites or the entire study are described in Appendix 1 (Section 10.1).

### 7.1. Discontinuation of IMP

### 7.1.1. Permanent Discontinuation

Permanent discontinuation of IMP occurs when the participant stops receiving the IMP before the end of the study, does not resume receiving IMP, and does not withdraw informed consent. The investigator will document the primary reason for early discontinuation of IMP. Participants who permanently discontinue IMP will complete the IMP discontinuation visit and will be encouraged to remain in the study and attend any previously scheduled visits. Blood samples for participants remaining in the study following IMP discontinuation will be collected for PK analyses as per the SoA (Section 1.3) for up to 3 weeks post IMP discontinuation.

If the participant is unable or unwilling to attend study visits for any reason, the study site will perform an EDV and the SFV. The study sites will attempt to perform the EDV within the 7 (+2) days after the participant's final IMP administration. The SFV will occur  $56 \pm 3$  days after the participant's final IMP administration.

Additionally, the following circumstances will result in the permanent discontinuation of IMP:

- The participant becomes pregnant or intends to become pregnant (refer to Section 8.3.5).
- The investigator considers discontinuing IMP is in the participant's best interest (the sponsor will be informed).
- The participant develops an SAE or AE that contraindicates further administration of IMP in the investigator's opinion or an AE of CTCAE severity grade 4 that is considered related to IMP by the sponsor.
- The participant receives a prohibited medication or substance (refer to Section 6.9).

Participants permanently discontinuing IMP will be ineligible for roll over to the OLE study.

## 7.1.2. Temporary Discontinuation

Temporary discontinuation occurs when the participant discontinues receiving IMP before the end of the study but may resume once the cause for the discontinuation has been resolved.

Reasons requiring temporary interruption may include an AE that meets the following criteria:

- Any SAE considered related to IMP by the sponsor
- Clinically significant active infection considered related to the IMP by the sponsor

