#### 2.3.1. Risk Assessment

Overall, available data confirm that efgartigimod IV has been well tolerated across studies in different indications and has an acceptable safety profile.

Potential clinically significant risk	Summary of data/ rationale for risk	Mitigation strategy
Serious infection	Efgartigimod reduces IgG levels, potentially hindering immune response and increasing the	Exclude participants with clinically significant uncontrolled infections (Section 5.2).
	infection risk.	Monitor for infections, considered an adverse event of special interest (AESI; Section 8.4.6), and temporarily interrupt IMP dosing as specified in Section 7.1.
Infusion-related reactions (IRR)	All therapeutic proteins have the potential to elicit immune responses, potentially resulting in hypersensitivity or allergic reactions such as rash, urticaria, angioedema, serum sickness, and anaphylactoid or anaphylactic reactions.	As with any IV infusion, the potential exists for IRR, which may occur during or within 48 hours after infusion.  Pretreatment to prevent an IRR is not required. IMP will be administered by a healthcare professional.

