## 5.2. Exclusion Criteria

Participants will be excluded from the study if any of the following criteria apply:

- 1. Known autoimmune disease or any medical condition that, in the investigator's judgment, would interfere with an accurate assessment of clinical symptoms of pSS or puts the participant at undue risk
- 2. History of malignancy unless considered cured by adequate treatment with no evidence of recurrence for  $\geq 3$  years before the first administration of IMP. Adequately treated participants with the following cancers may be included at any time:
  - a. Basal cell or squamous cell skin cancer
  - b. Carcinoma in situ of the cervix
  - c. Carcinoma in situ of the breast
  - d. Incidental histological finding of prostate cancer (TNM stage T1a or T1b)
- 3. Clinically significant uncontrolled active acute or chronic bacterial, viral, or fungal infection
- 4. Positive serum test at screening for an active infection with any of the following:
  - a. HBV that is indicative of an acute or chronic infection, unless associated with a negative HBsAg or negative HBV DNA test
  - b. HCV based on HCV antibody assay unless a negative RNA test is available

- c. HIV based on test results of a CD4 count of < 200 cells/mm^3 that are associated with an AIDS-defining condition
- d. HIV based on test results of a CD4 count of ≥200 cells/mm³ not adequately treated with antiviral therapy
- 5. Clinically significant disease, recent major surgery (within 3 months of screening), or intention to have surgery during the study; or any other medical condition that, in the investigator's opinion, would confound the results of the study or put the participant at undue risk
- 6. Current participation in another interventional clinical study
- 7. Known hypersensitivity to IMP or 1 of its excipients
- 8. History (within 12 months of screening) of current alcohol, drug, or medication abuse as assessed by the investigator
- 9. Pregnant or lactating state or intention to become pregnant during the study
- 10. Previously participation in an efgartigimod clinical study and treatment with  $\geq 1$  dose of IMP
- 11. Total IgG of < 4 g/L at screening
- 12. Secondary Sjögren's syndrome overlap syndromes where another confirmed autoimmune rheumatic or systemic inflammatory condition (eg, rheumatoid arthritis, systemic lupus erythematosus, scleroderma, inflammatory bowel disease) is the primary diagnosis
- 13. Positive SARS-CoV-2 PCR test at screening

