## 8.4.6. Adverse Events of Special Interest

An AESI is an event of scientific and medical concern specific to the sponsor's product or program. An AESI can be serious or nonserious, related or unrelated to the IMP or study procedures. These events will be reported according to the timeframe specified in Section 8.4.1 and Section 10.3.4.

Efgartigimod treatment leads to reduced IgG levels. As low IgG levels are associated with increased infection risks, events in the MedDRA SOC Infections and Infestations are considered AESIs in this study. These events will be reported according to the timeframe specified in Section 8.4.1 and Section 10.3.4, with the following information provided:

- Causal pathogen
- Location of infection
- Relationship to an underlying medical condition, medical history, and concomitant medications
- Reoccurrence of a previous infection
- Any confirmatory procedure, culture, or urgent medical intervention

Participants for whom an AESI has been reported may be temporarily interrupted from IMP treatment, as specified in Section 7.1.1.

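### Protocol 7.1.2 lists infection as a reason to pause dosing only if the sponsor considers it related to IMP; pauses for other infections are discretionary, and two cross-references for a pause point to the permanent-stop section

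*Protocol*

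**What the plan says.** Protocol 7.1.2 is the only section on temporary discontinuation. Its list opens with "Reasons requiring temporary interruption may include an AE that meets the following criteria", and two criteria follow: "Any SAE considered related to IMP by the sponsor" and "Clinically significant active infection considered related to the IMP by the sponsor". Both depend on the sponsor's view of causality.

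Three other parts of the protocol deal with infection:

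- The risk table (2.3.1) names serious infection as a potential risk of lowering IgG. Its mitigation is to monitor for infections and "temporarily interrupt IMP dosing as specified in Section 7.1".
- Exclusion criterion 3 (5.2) bars entry with "Clinically significant uncontrolled active acute or chronic bacterial, viral, or fungal infection", whatever the cause.
- Section 8.4.6 makes every event in the infections system organ class an AESI and adds "An AESI can be serious or nonserious, related or unrelated to the IMP or study procedures". It then says "Participants for whom an AESI has been reported may be temporarily interrupted from IMP treatment, as specified in Section 7.1.1".

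Section 6.7, on OLE entry, refers to participants who reach week 24 "temporarily interrupted from IMP (refer to Section 7.1.1". Section 7.1.1 is headed Permanent Discontinuation. It covers permanent stops and the visits that follow them, and has no rule for pausing or restarting.

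**The concern.** When an infection is active, the clinical question is whether to give another IgG-lowering dose into it. That question does not depend on whether the drug caused the infection. Section 7.1.2 nevertheless ties its infection reason to a causality call, and the call belongs to the sponsor rather than the physician seeing the participant. A serious infection does not escape through the SAE reason, because that has the same condition.

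The stake is participant safety. If the sponsor is undecided or considers the infection unrelated, no listed reason applies and the next weekly dose rests on site discretion. A site that follows the AESI section to find out how to pause is sent to rules that describe only a permanent stop. A permanent stop bars OLE entry (6.7, 7.1.1), and the SAP's main estimand counts it as nonresponse (Table B). A plain rule also has practical value here: 16 of the 24 dosing visits may take place at home (Schedule of Activities, visits 4, 6-8, 10-12, 14-16, 18-20 and 22-24), and there is no data monitoring committee.

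**Working it through.** The finding itself is textual, so the first step is to set the sections side by side.

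| Section | Subject | Relatedness needed? | Force |
|---|---|---|---|
| 2.3.1 | Mitigation for serious infection | None of its own; cites 7.1 | Listed mitigation |
| 5.2, criterion 3 | Entry with uncontrolled infection | No | Mandatory exclusion |
| 7.1.2, first reason | SAE | Yes, per sponsor | Listed reason under an open lead-in |
| 7.1.2, second reason | Clinically significant active infection | Yes, per sponsor | Listed reason under an open lead-in |
| 8.4.6 | Any infection, as an AESI | No | Discretionary; cites 7.1.1 |
| 6.7 | Participants paused at week 24 | Not applicable | Cites 7.1.1 |
| 7.1.1 | Stopping IMP | Varies by reason | Permanent stop only |

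Three things follow. No infection reason in 7.1.2 is free of the sponsor's causality call. The section that covers infections regardless of cause (8.4.6) is discretionary and gives no criteria. Its pointer and the one in 6.7 name the wrong subsection. The pointer in 2.3.1 to the parent Section 7.1 is acceptable.

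**Size.** The plan gives no infection rate and no figure to reproduce. The following are assumptions: 5% to 20% of participants have a clinically significant active infection during dosing; 50% to 90% of these infections are undecided or judged unrelated; each lasts 7 to 14 days, so 1 to 2 weekly doses fall due. The infection rate is taken as equal in both arms.

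From the documents: about 30 participants (15 per IgG stratum), of whom about 20 are on efgartigimod (2:1), with 24 weekly doses each. Planned doses are 30 × 24 = 720 in total and 20 × 24 = 480 of efgartigimod.

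Participants outside the listed reason = N × infection rate × share undecided or unrelated:

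| Infection rate | Share | Of 30 | Of about 20 on efgartigimod |
|---|---|---|---|
| 5% | 50% | 0.75 | 0.5 |
| 5% | 90% | 1.35 | 0.9 |
| 10% | 50% | 1.5 | 1.0 |
| 10% | 90% | 2.7 | 1.8 |
| 20% | 50% | 3.0 | 2.0 |
| 20% | 90% | 5.4 | 3.6 |

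Doses falling due = participants × 1 or 2:

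- All participants: 0.75 × 1 = 0.75 to 5.4 × 2 = 10.8 of 720 (0.1% to 1.5%).
- Efgartigimod only: 0.5 × 1 = 0.5 to 3.6 × 2 = 7.2 of 480 (0.1% to 1.5%).

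The safety concern relates to the efgartigimod figures. The total measures the cost of a hold applied in both arms.

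**The case against.** The strongest reply is that the protocol already allows the pause. The lead-in to 7.1.2 is open, its definition of temporary discontinuation carries no causality condition, and 8.4.6 lets any reported AESI lead to an interruption. SAP 18.1 tabulates TEAEs leading to interruption separately from treatment-related TEAEs, so the analysis does not treat interruption as confined to related events. A list for sponsor-related events with investigator judgment for the rest is a coherent structure. This stands: a reader might infer that the protocol forbids holding a dose for an unrelated infection, and it does not. What is missing is any text that calls for the hold.

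A reader might also infer that the causality test would class many infections as not related, because 10.3.3 gives concomitant therapy as an alternative explanation and oral corticosteroids up to 10 mg are allowed. The documents do not support that. The same definition of not related also rules out any plausible temporal or biologic relationship, while 2.3.1 and 8.4.6 themselves describe a biologic link between low IgG and infection. The definition of related is demanding too, so the text settles the matter in neither direction. Moreover, 10.3.3 is written for the investigator, whereas 7.1.2 turns on the sponsor's view.

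The wrong pointers can fairly be called editorial. Section 7.1.2 follows 7.1.1 directly under a plain title, and a site is unlikely to apply permanent-stop rules to someone described as temporarily interrupted.

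Other safeguards also exist. AESIs reach the sponsor within 24 hours (8.4.1), the investigator or designee interviews the participant for each home visit (10.6), and the investigator may stop IMP in the participant's best interest, though only permanently (7.1.1). These reduce the risk without saying when to hold. Finally, 2.3.1 defers to Section 7.1, so it can be read as importing the condition in 7.1.2. On that reading the mitigation for the named risk is narrower than the table suggests, which is itself a reason to align the two.

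**Conclusion.** The point holds as a gap in a safety rule. The listed reasons for a pause depend on sponsor-assessed relatedness; infections that are undecided or judged unrelated are left to discretion; and two cross-references are wrong. All of this is in the current text and does not depend on the assumed rates.

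The size does depend on them: about 0.5 to 3.6 efgartigimod participants and 0.5 to 7.2 of 480 efgartigimod doses, within 0.75 to 5.4 participants and 0.75 to 10.8 of 720 doses overall. These are upper limits for each set of assumptions, because they count every dose falling due as though no investigator used the pause already available. A reader might look for a consequence for the CRESS result. None is claimed, and nothing here alters the sample size or the planned precision.

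**What to change.** 1. In Protocol 7.1.2, take infection out of the permissive list and give it its own sentence: *IMP will be held for any clinically significant active infection, as judged by the investigator or the sponsor, whether or not considered related to IMP, until the infection has resolved or is controlled.* Keep the related-SAE reason as it is. Naming the sponsor as an alternative trigger means that no infection now listed is lost, and a separate sentence is needed because a firm hold placed under the present lead-in would still read as optional.
2. In 8.4.6 and 6.7, change the cross-reference from 7.1.1 to 7.1.2.

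This needs no new visit, sample, committee, IgG result or unblinding, and the rule is the same in both arms. The cost is at most the extra held doses sized above. For one participant, a held dose is 1/24 = 4.2% of the course; four missed doses leave 20/24 = 83.3%, and it takes five (19/24 = 79.2%) to enter the SAP's below-80 compliance category. Section 6.5 already handles a missed dose by waiting for the next scheduled one, and 6.7 lets a participant paused at week 24 enter the OLE at the investigator's discretion. A temporary hold is not among the intercurrent events named in SAP Table B.

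A hold close to week 24 could slightly affect efficacy items at that visit. The CRESS serology item has a wide margin, since it needs a 10% fall in IgG against about 70% expected (8.2.1, 4.3). ESSPRI, with its two-week recall, clinESSDAI and the glandular items have no comparable margin to cite, so a small effect on them cannot be excluded.
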